6.2. Blinded data review

Prior to unmasking the study and starting any formal analysis, data will be reviewed in a blinded fashion by computing summary statistics for primary and secondary outcomes, and baseline covariates. This will allow the identification of unusual values and/or patterns of missing values for key variables that need to be queried. In addition, such blinded data review will allow the writing committee to assess the format of data presentation. Note that the blinded data review incorporates real data but *random* treatment assignment (i.e., investigators do not receive data summarized by actual treatment group, rather they review data on two randomly formed groups). All decisions will be made and documented in this SAP document prior to database lock and unblinding.

6.3. Visit windows

To provide scheduling flexibility to study sites and participants, visits were required to occur within a protocol-defined window rather than on a specific date. The protocol-defined visit windows are summarized in the tables 6.3.1 and 6.3.2 below. For analytic purposes, the visit windows defined in the protocol will be expanded in order to eliminate gaps between them. This will ensure that all observations, including those that may have occurred outside a protocol-specified time window, will be associated with the most appropriate visit and therefore properly included in the analysis. If multiple observations occur within a window, the one closest to the visit target date will be utilized. If two observations are equi-distant from the target date, the first one will be utilized.

As iGFR is the primary and key secondary endpoint, the protocol allowed for repeats of the iGFR procedure in order to achieve qualified iGFR values. Also, the procedure required a longer visit, so it was more difficult to schedule. Thus, we allowed wider windows for iGFR visits (V11, V16 and V17) to ensure that all qualified iGFRs are analyzed. In addition to avoid over-writing iGFR visits with a non-iGFR (V6-V10, V12-V15) visit, and vice-versa the aforementioned procedure will be performed separately for non-iGFR (Table 6.3.1) and iGFR visits (Table 6.3.2).

Table 6.3.1. PERL windows for post-randomization non-IGFR visits.

Visit	Lower Boundary of Window (Week, Excluding First day)	Per protocol Target Date window in weeks	Upper Boundary of Window (Week, Including last day)	Time since randomization attributed to visit window (in weeks)
Visit Windows relative to Randomization Date				
Visit 6	0	4 [3-5]	10	5
Visit 7	10	16 [14-20]	24	17
Visit 8	24	32 [30-34]	40	32
Visit 9	40	48 [46-50]	56	48
Visit 10	56	64 [62-66]	72	64
Visit 12	88	96 [94-98]	104	96
Visit 13	104	112 [110 -114]	120	112
Visit 14	120	128 [126 -130]	135	128
Visit 15	135	142 [140 -146]	150	142

All intervals (target dates and lower/upper window boundaries) for visits 6 through 16 are calculated relative to the randomization date. The interval for Visit 17 is calculated relative to Visit 16. Most post-randomization visits are 16 weeks apart, with the exception of Visits 6 and 7 and Visits 16 to visit 17. For the purpose of selected analyses (sections 6.7.2 and 6.7.4) involving multiple imputations, we included in the last column of Tables 6.3.1 and 6.3.2 a time since randomization associated with a corresponding visit window. Entries in this column are based approximately on the mid-points between target dates.

Table 6.3.2. PERL windows for post-randomization iGFR visits.

Visit	Lower Boundary of Window (Week, Excluding First day)	Per protocol Target Date window in weeks	Upper Boundary of Window (Week, Including last day)	Time since randomization associated with visit window (in weeks)
Visit Windows relative to Randomization Date				
Visit 11 (iGFR)	53	80 [78-84]	97	80
Visit 16 (iGFR)	149	156 [154 -160]	178	164
Visit Window relative to V16				
Visit 17 (iGFR)	0	8 [6-12]	20	174

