3.4. Calculations of visit windows for the analytical dataset

RATIONALE:

Per-protocol windows for scheduling Visits 6-16 are calculated relative to the Visit 5 date. In early versions of the Study Protocol (versions 5.0 and 6.0), randomization was performed at a study visit (Visit 5) and consequently the visit date and randomization date were equivalent. Starting with Study Protocol, version 7.0, Visit 5 became a phone call visit and randomization did not necessarily occur on the date of the phone call. For analytical purposes (see SAP Section 6.3), visit windows will be calculated relative to randomization date.

PROTOCOL:

Visit 1 will be considered as Time 0 for scheduling Visits 2-5, Visit 5 will be considered as Time 0 for scheduling Visit 6-16, Visit 16 as Time 0 for scheduling Visit 17.

SAP:

Visit 1 will be considered as Time 0 for scheduling Visits 2-5, Visit 5 will be considered as Time 0 for scheduling Visit 6-16, Visit 16 as Time 0 for scheduling Visit 17. For analytical purposes, the randomization date will be considered as Time 0 for calculating windows for Visits 6-16.

3.5. Additional analysis assessing an effect of post-randomization serum uric acid changes on iGFR values at Visit 17

RATIONALE:

Following internal discussion on the importance of the relationship between serum uric acid (sUA) and iGFR measures, we added this analysis.

PROTOCOL:

Not applicable

SAP:

Details are provided in SAP Section 6.8.4.

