3.8. Modifying definition of per-protocol analysis set

RATIONALE:

Following internal discussion we modified the per-protocol definition as follows.

PROTOCOL:

- **Per Protocol:** ... The per protocol population will exclude subjects ... as well as data points for which the cumulative exposure to the study medication from

randomization to that time point was less than 80% of the theoretical full exposure (see Section 11.1 in the protocol).

SAP:

- **Per Protocol:** ... The per protocol population will exclude subjects ... for whom the average drug exposure was less than 80% (see Section 11.1 in the protocol).

4. Study Aim

The study aim is to determine whether lowering serum UA by means of oral allopurinol is effective in preventing or slowing decline of renal function in T1D patients with history and/or presence of microalbuminuria or moderate macroalbuminuria, or with ongoing GFR loss regardless of history or presence of albuminuria, who have only mildly or moderately impaired kidney function.

5. Study Estimands

This section describes the primary and secondary estimands for corresponding endpoints and variables of interest. We follow ICH-E9 (R1) recommendations and specify estimands in terms of four attributes defining the treatment effect of interest:

- A1. The target population
- A2. The variable (or endpoint) to be obtained for each patient that is required to address scientific question of interest
- A3. Strategies for addressing intercurrent events
- A4. The population summary for the variable (endpoint), that provides a basis for a comparison between treatment conditions.

In Table 5.1. we include various intercurrent events that occurred in the PERL study and divide them into three groups, based on their implications for subsequent data collection of the endpoint of interest.

Table 5.1. Groups of intercurrent (IC) events in PERL study

Group of IC events	IC event	Implications for Post-IC data
Group A	Non-adherence to study drug schedule	Post-IC data are collected, but their interpretation may be affected depending on the estimand of interest
	Permanent discontinuation of study drug	
	Use of prohibited medication	
	Missed scheduled visit	
Group B	ESRD treatment (hemodialysis or transplant for ESRD subjects)	Post-IC data do not contain any relevant information about estimands of interest and for this reason they are not collected
Group C	Early discontinuation from the study	Post-IC data cannot be collected
	Terminal event, i.e. death	

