5.1. Primary estimand for iGFR at Visit 17 endpoint

This is the de-facto (effectiveness) estimand of the primary endpoint – iGFR at Visit 17 – that quantifies a treatment effect due to the initially randomized treatments as actually taken, i.e., the treatment of allopurinol versus placebo without a confounding effect of treatment for ESRD subjects. The four attributes of this estimand are as follows:

A1. Target population: Individuals with T1D meeting the inclusion/exclusion criteria specified in the Study Protocol.

A2. The variable (or endpoint): The primary endpoint is the measured glomerular filtration rate (GFR) based on plasma disappearance of non-radioactive iohexol (iGFR) at the end of the 2-month wash-out period (Visit 17 at Week 164) following the 3-year intervention. The rationale of measuring the primary outcome at the end of the wash-out period is to test allopurinol for *durable* effects on the natural history of kidney disease, independent from any transient, hemodynamic effect that the medication may have on GFR. iGFR is calculated from blood samples drawn at baseline and 120, 150, 180, 210, and 240 minutes after an i.v. bolus of iohexol, adjusting for body surface area.

A3. Strategies for different groups of IC events: Depending on IC event group membership (see Table 5.1), the variable of interest, in this case iGFR values, collected after an IC event in

- Group A will be considered as directly interpretable. Effectively, IC events in this group are ignored, which is consistent with the ITT principle.
- Group B are assumed to follow a hypothetical scenario, in which variable of interest after developing ESRD takes on biologically plausible values that are not confounded by IC event i.e. by ESRD treatment.
- Group C are assumed to conform to a hypothetical scenario in which post-IC values of the variable of interest (or endpoint) have a similar distribution to other non-ESRD subjects

A4. Population summary to compare treatments: Population-average treatment effect on iGFR at V17.

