6.7. Analyses for secondary estimands

In this section we present analyses aligned with secondary estimands defined in section 5.2. Analyses will be performed using the multiple imputation technique, except those involving time-to event endpoints (sections 6.7.5, 6.7.8).

6.7.1. iGFR at the end of the 3-year treatment period (Visit 16, before the washout)

In this section we describe the analysis (estimator) aligned with the estimand for iGFR at the end of the 3-year treatment period (Visit 16, before the washout) endpoint defined in Section 5.2.1.

The least square means at Visit 16, estimate of treatment effect *at Visit 16* adjusted for baseline covariates, their 95% confidence interval and P-value will be obtained as part of the primary analysis of the primary estimand (Equation (6.1) in section 6.1.1). In the context of this secondary endpoint, we are interested in the fixed effect β_{12} , which represents the treatment effect at Visit 16 adjusted for stratifying variables and baseline covariates. To assess the hemodynamic/transient effect of the allopurinol, we will estimate the contrast $\beta_{12} - \beta_{13}$ between the treatment effect at Visit 16 (before washout) compared to that at Visit 17 (after washout).

6.7.2. iGFR time trajectory estimated from repeated iGFR measurements

This analysis is aligned with the estimand defined in Section 5.2.2

Estimand	See section. 5.2.2 for definition
Analysis	Analysis of the Secondary Endpoint: iGFR time trajectory estimated from repeated iGFR measurements.
Analysis Set	ITT Population
Methods	Linear mixed-effects model for longitudinal iGFR measures using multiple imputation technique.
Dependent Variable	iGFR measured at Visits V11 (80 weeks) , V16 (156 weeks) and V17 (164 weeks after randomization)
Model	
Fixed effects associated with:
 
 • Stratifying variables: sUA, HbA1c, study center • Treatment group • Time since randomization (in years) associated visit windows defined in section 6.3 • Time by treatment group interaction • Albuminuria status with 2 levels • Baseline AER geometric mean (at Visits 3 and 4 combined) expressed on log to base 10 scale • Baseline iGFR 
Subject-specific random effects
 
 • Random intercept for iGFR • Random slope for iGFR

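### SAP 6.3 assigns iGFR tests by date window, so when Visit 16 was missed a measured week-164 washout test is labelled Visit 16 and the primary endpoint is imputed

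*SAP*

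**What the plan says.** SAP 6.3 widens the protocol windows for analysis so that no gaps remain, and settles competing tests by date: "If multiple observations occur within a window, the one closest to the visit target date will be utilized". Ties go to the earlier test.

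In Table 6.3.2 the Visit 16 target is week 156 and its analysis window runs from after week 149 to week 178. SAP 3.4 sets time zero: "For analytical purposes, the randomization date will be considered as Time 0 for calculating windows for Visits 6-16". For Visit 17, "The interval for Visit 17 is calculated relative to Visit 16", with target 8 weeks and a window from after 0 to 20 weeks. No rule covers an absent Visit 16.

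The only protection against one visit displacing another is this: "In addition to avoid over-writing iGFR visits with a non-iGFR (V6-V10, V12-V15) visit, and vice-versa the aforementioned procedure will be performed separately". It separates iGFR visits from non-iGFR visits. It does not separate Visit 16 from Visit 17.

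SAP 5.1 places the primary endpoint "at the end of the 2-month wash-out period (Visit 17 at Week 164) following the 3-year intervention". Table 5.1 lists "Missed scheduled visit" among the Group A intercurrent events, and of values collected after such events SAP 5.1 says "Group A will be considered as directly interpretable". Missing iGFR values are multiply imputed under SAP 6.5.

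**The concern.** Visit 16 is the last on-treatment iGFR and Visit 17 is the washout iGFR. The design relies on the difference between them, because the primary outcome is measured after washout to remove any transient haemodynamic effect. A rule that uses dates and ignores the recorded visit can confuse the two.

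If it does, a measured primary endpoint is replaced by an imputed one, against the SAP's own treatment of missed visits. An off-drug value can also enter the Visit 16 treatment effect and the comparison of Visits 16 and 17 in SAP 6.7.1: "To assess the hemodynamic/transient effect of the allopurinol, we will estimate the contrast".

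The situation is foreseeable. Protocol 5.5.2 keeps participants who have stopped study drug in follow-up to week 164, so someone already off drug could miss Visit 16 and still attend for the washout test.

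**Working it through.** **Inputs.** Protocol 8.1: Visits 16 and 17 may be held from 2 weeks before to 4 weeks after their scheduled dates. Table 6.3.2: Visit 16 target 156, window (149, 178]; Visit 17 target 8 weeks after Visit 16, window (0, 20].

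**1. Reproduce the table.** 156 − 2 = 154 and 156 + 4 = 160. 8 − 2 = 6 and 8 + 4 = 12. These match the protocol windows [154–160] and [6–12] printed in Table 6.3.2.

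**2. Overlap.** On-schedule washout tests run from 154 + 6 = 160 to 160 + 12 = 172 weeks. All lie inside (149, 178].

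**3. Visit 16 missed.** Assume the washout test is held at its scheduled week 164 with the protocol tolerance.
- The permitted dates are 164 − 2 = 162 to 164 + 4 = 168 weeks, which is 6 × 7 + 1 = 43 days.
- All 43 fall in (149, 178], so the rule labels the test Visit 16.
- Visit 17 then has no test. Either it has no Visit 16 date to count from, or the washout test itself has become Visit 16 and nothing follows it. Both readings leave Visit 17 empty, and SAP 6.5 imputes it.

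**4. Both visits attended, on schedule, no repeats.** Let Visit 16 be a weeks before week 156 and the washout test e weeks after Visit 16.
- The washout test takes the Visit 16 slot only if |e − a| < a, that is, e < 2a.
- Within protocol windows a ≤ 2 and e ≥ 6, so 2a ≤ 4 and the condition cannot be met.
- Day-by-day enumeration agrees: 0 of 43 × 43 = 1,849 pairs are misassigned.

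**5. Both visits attended, Visit 16 early.** Take tests at weeks 152 and 159, so a = 4 and e = 7 < 8.
- Both lie in (149, 178]. Their distances from 156 are 4 and 3, so week 159 becomes Visit 16.
- No later test remains, so Visit 17 is empty.

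**6. Repeats (secondary).** After an iGFR fall of more than 20% per year that eGFR does not match, protocol 13.5.b.7.l keeps the first value if the fall is confirmed. It also keeps the first value if the fall is not confirmed and no reason to postpone the test is found.
- With a first Visit 17 test f weeks after Visit 16 and a repeat d weeks later, the date rule takes the repeat when |f + d − 8| < |f − 8|, that is, f < 8 − d/2.
- Over the 43 permitted days (f from 6 to 12 weeks) this is 7 days for d = 2, 4 for d = 3 and 0 for d = 4.
- These intervals are assumed, because the documents set no time limit for this repeat.

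**7. After the fix.** With the recorded visit used first, the case in step 3 gives Visit 16 missing and Visit 17 observed. The case in step 5 gives Visit 16 = week 152 and Visit 17 = week 159.

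**The case against.** The strongest reply is that SAP 6.3 never says recorded visits are ignored, states that each observation should end up with the visit that suits it best, and is followed by SAP 6.6.1, which labels Visit 17 as week 164. A sensible programmer would then keep the test as Visit 17. That is fair as to intent, but these are a purpose and a label. The only written assignment rule is the window rule, and it gives the other answer.

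Three further replies stand in part:
- The scenario is narrow. Protocol 8.6 gives the stop-drug instruction at Visit 16, so someone who missed that visit may still be on drug at week 164, and the test may properly be a late Visit 16. Dates alone cannot tell the two apart.
- The value is not wholly lost. As a Visit 16 value it enters the imputation model and informs the imputed Visit 17.
- The blinded data review in SAP 6.2 looks for patterns of missing values and might catch the case.

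Two stronger readings are tempting and are not supported:
- A reader might infer that the SAP has overridden protocol 13.5.b.7.l without declaring it. SAP Section 3 lists changes from the protocol, and its silence on this item may equally mean that the item still governs and the windows apply to the value it selects.
- A reader might take the last column of Table 6.3.2, which gives week 164 for Visit 16 and 174 for Visit 17, as confirmation of mislabelling. SAP 6.3 reserves that column for the slope models in 6.7.2 and 6.7.4, so it has no bearing on assignment.

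**Conclusion.** The point holds as a stated rule that gives a wrong result in identifiable cases, and it should be fixed. With Visit 16 missed, every permitted washout date (43 of 43) is labelled Visit 16 and the measured primary endpoint is imputed, contrary to SAP 5.1 and Table 5.1. With Visit 16 well before its protocol window, the same can happen although both tests were done.

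The 43 of 43 describes the calendar and is not a frequency. The documents give no count of missed Visit 16 tests or of repeats, so the effect on the estimate cannot be sized; the number affected is probably small. A reader might infer a general mislabelling of the endpoint or a bias towards one arm. The documents support neither: 0 of 1,849 on-schedule pairs without repeats is misassigned, and the rule is blind to arm.

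The conclusion assumes that SAP 6.3 is applied literally and, for the main case, that the washout test keeps its scheduled week when Visit 16 is missed. The repeat issue is secondary and depends on assumed intervals and on how the SAP's silence is read.

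**What to change.** In SAP 6.3, before database lock:

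1. Assign iGFR tests to Visit 16 or Visit 17 by the recorded (nominal) visit first. Use date windows only for tests without a usable visit label. Never use one test for two visits.
2. If Visit 16 was missed, keep a test recorded as Visit 17 as Visit 17. For an unlabelled test, anchor to the recorded drug-stop date where one exists. Otherwise settle the label in the blinded data review and document it. A fixed week-156 anchor is not a safe default: its window, 156 to 156 + 20 = 176 weeks, could label a late on-drug test as washout.
3. Add one sentence that the first-or-repeat choice in protocol 7.1.3 and 13.5.b.7.l is made before the closest-to-target rule.

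The cost is a few lines of SAP text and programming. The change is blind to arm and alters no trial procedure. It does assume that the visit under which each test was recorded is available in the database, which should be confirmed. Protocol 5.5.2 provides for recording the date of drug discontinuation but does not clearly cover the planned stop at the end of treatment, so some unlabelled tests may need individual review.

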Results	
 • iGFR slope estimates and 95%CIs by treatment group • Estimate of a treatment effect measured as a difference between average slopes of iGFR versus time for allopurinol and placebo groups adjusted

	for stratifying variables and baseline covariates 
 • 95% confidence interval for treatment effect • P-value for treatment effect
--	--

6.7.3. eGFR at 4 months after randomization (Visit 7)

Estimand	See section 5.2.3 for definition
Analysis	Analysis of the Secondary Endpoint: eGFR at 4 months after randomization (Visit 7).
Analysis Set	ITT Population
Methods	Linear model using multiple imputation technique.
Dependent Variable	eGFR measured at Visit V7 (16 weeks after randomization)
Model	Fixed effects associated with: 
 • Stratifying variables: sUA, HbA1c, study center • Treatment group • Albuminuria status with 2 levels • Baseline AER geometric mean (at Visits 3 and 4 combined) expressed on log to base 10 scale • Baseline eGFR
Results	
 • Least square eGFR means at Visit 7 by treatment group. • Estimate of treatment effect at Visit 7 adjusted for stratifying variables and baseline covariates • 95% confidence interval for treatment effect • P-value for treatment effect

6.7.4. eGFR time trajectory

Estimand	See section 5.2.4 for definition
Analysis	Analysis of the Secondary Endpoint: eGFR time trajectory estimated from repeated eGFR measurements using multiple imputation technique..
Analysis Set	ITT Population
Methods	Linear mixed-effects model for longitudinal eGFR measures using multiple imputation technique.
Dependent Variable	Post-randomization eGFR measured from Visits V6 through V17
Model	Fixed effects associated with: 
 • Stratifying variables: sUA, HbA1c, study center • Treatment group • Time since randomization in (in years) associated visit windows defined in section 6.3 • Time by treatment group interaction • Albuminuria status with 2 levels • Baseline AER geometric mean (at Visits 3 and 4 combined) expressed on log to base 10 scale • Baseline eGFR Subject-specific random effects 
 • Random intercept for eGFR • Random slope for eGFR

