6.6. Analyses of Secondary Endpoints

6.6.1. iGFR at the end of the 3-year treatment period (Visit 16, before the washout)

The predicted means at Visit 16, estimate of treatment effect *at Visit 16* adjusted for baseline covariates, their 95% confidence interval and P-value will be obtained as part of the primary analysis of the primary endpoint (Equation (6.1) in section 6.1.1). In the context of this secondary endpoint, we are interested in fixed effect β_{12} , which represents treatment effect at Visit 16 adjusted for stratifying variables and baseline covariates.

6.6.2. iGFR time trajectory estimated from repeated iGFR measurements

Analysis	Analysis of the Secondary Endpoint: iGFR time trajectory estimated from repeated iGFR measurements
Analysis Set	mITT Population
Methods	Linear mixed-effects model for longitudinal iGFR measures
Dependent Variable	iGFR measured at Visits V11 (80 weeks), V16 (156 weeks) and V17 (164 weeks after randomization)
Model	
Fixed effects associated with:
 
 • Stratifying variables: sUA, HbA1c, study center • Treatment group • Time since randomization in days • Time by treatment group interaction • Albuminuria status with 2 levels • Baseline AER geometric mean (at Visits 3 and 4 combined) expressed on log to base 10 scale • Baseline iGFR 
Subject-specific random effects
 
 • Random intercept for iGFR • Random slope for iGFR
Results	
 • iGFR slope estimates and 95% CIs by treatment group • Estimate of a treatment effect measured as a difference between average slopes of iGFR versus time for allopurinol and placebo groups adjusted for stratifying variables and baseline covariates • 95% confidence interval for treatment effect • P-value for treatment effect

6.6.3. eGFR at 4 months after randomization (Visit 7)

Analysis	Analysis of the Secondary Endpoint: eGFR at 4 months after randomization (Visit 7)
-----------------	--

Analysis Set	mITT Population
Methods	Linear model
Dependent Variable	eGFR measured at Visit V7 (16 weeks after randomization)
Model	Fixed effects associated with: 
 • Stratifying variables: sUA, HbA1c, study center • Treatment group • Albuminuria status with 2 levels • Baseline AER geometric mean (at Visits 3 and 4 combined) expressed on log to base 10 scale • Baseline eGFR

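### Table 6.3.2 places Visits 16 and 17 at weeks 164 and 174 for the slope models, against its own targets of 156 and 164; with visits on schedule, iGFR slopes and their difference come out about 10% too small.

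*SAP*

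**What the plan says.** SAP 6.3 widens the protocol visit windows for analysis and adds a column giving one time since randomization per visit, for use in 6.7.2 and 6.7.4. It describes the column so: "Entries in this column are based approximately on the mid-points between target dates". The rows of Table 6.3.2 (lower bound, target with protocol window, upper bound, assigned time, all in weeks) include "Visit 11 (iGFR) 53 80 [78-84] 97 80" and "Visit 16 (iGFR) 149 156 [154 -160] 178 164". Visit 17 has a target of 8 [6-12] weeks after Visit 16, a window of 0 to 20 weeks after Visit 16, and an assigned time of 174.

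The iGFR slope model in 6.7.2 has as its time covariate "Time since randomization (in years) associated visit windows defined in section 6.3"; the eGFR slope model in 6.7.4 has "Time since randomization in (in years) associated visit windows defined in section 6.3". Yet 6.7.2 describes its own dependent variable as measured at Visit 11 (80 weeks), "V16 (156 weeks) and V17 (164 weeks after randomization". The schedule of events in Protocol 8.1 also gives weeks 80, 156 and 164.

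The superseded SAP of February 22, 2017 used "Time since randomization in days" in both slope models (its 6.6.2 and 6.6.4).

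**The concern.** A slope per year is only as good as the time axis. Here two of the three iGFR visits are moved 8 and 10 weeks later than target while the first stays put. Both assigned times lie beyond the latest dates the protocol allows: week 160 for Visit 16, and week 160 + 12 = 172 for Visit 17. No observed visit times are offered in support. Where several observations fall in one window, 6.3 keeps the one nearest the target date, which pulls towards 156 and not 164.

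At stake are secondary endpoints 2 and 4, reported as slopes by arm and a slope difference, each with a 95% confidence interval. A stretched axis pulls all of these towards zero. They then understate both the decline and the largest benefit compatible with the data, and sit awkwardly beside the planning values of 3 and 2 ml/min/1.73 m² per year in Protocol 11.10.

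**Working it through.** **1. Where 164 and 174 come from.**

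| Visit | Target (week) | Analysis window | Window mid-point | Assigned |
|---|---|---|---|---|
| V11 | 80 | 53-97 | 75 | 80 |
| V16 | 156 | 149-178 | 163.5 | 164 |
| V17 | 156 + 8 = 164 | V16 + 0 to 20 | 164 + 10 = 174 | 174 |

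The stated rule, mid-points between target dates, gives (142 + 156)/2 = 149 and (156 + 164)/2 = 160 around Visit 16: neither is 164. The mid-point of the widened window reproduces both V16 and V17. It also reproduces all nine entries of Table 6.3.1 to within half a week (for example V6: (0 + 10)/2 = 5; V7: (10 + 24)/2 = 17; V14: (120 + 135)/2 = 127.5, assigned 128). Visit 11 is the one exception.

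**2. Effect on the iGFR slope.** After imputation every participant has the same three assigned times. If measurements were taken at mean times t but analysed at times a, the estimated slope is the true slope multiplied by

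Σ(t − t̄)(a − ā) / Σ(a − ā)².

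With t = 80, 156, 164 (mean 133.33) and a = 80, 164, 174 (mean 139.33):

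- numerator: 53.33×59.33 + 22.67×24.67 + 30.67×34.67 = 4786.7
- denominator: 59.33² + 24.67² + 34.67² = 5330.7
- factor: 4786.7/5330.7 = **0.898**

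Two-point checks agree: V11 to V16, 76/84 = 0.905; V11 to V17, 84/94 = 0.894.

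Applied to the planning values in Protocol 11.10: −3.0 × 0.898 = −2.69; −2.0 × 0.898 = −1.80; a difference of 1.0 becomes 0.90.

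**3. Dependence on actual timing.** The documents hold no visit dates, so the true mean times below are assumptions.

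| True mean times V11/V16/V17 (weeks) | Factor |
|---|---|
| 80/156/164 (on target) | 0.898 |
| 84/160/172 (latest protocol dates) | 0.924 |
| 80/160/170 | 0.955 |
| 80/162/172 | 0.978 |
| 80/164/174 (as assigned) | 1.000 |
| 75/164/174 (all at window mid-points) | 1.056 |

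Over all combinations of V11 in {78, 80, 84}, V16 in {154, 156, 160} and the V16-V17 gap in {6, 8, 12}, the factor runs from 0.818 (84/154/160) to 0.991 (78/160/172). It stays below 1 throughout.

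**4. eGFR slope.** The same formula over Visits 6 to 17, targets 4, 16, 32, …, 142, 156, 164 against assigned 5, 17, 32, …, 142, 164, 174, gives 0.963, or 3.7% too small.

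**5. Inference.** Generalised least squares with random intercept and slope, 265 per arm and a true difference of 1.0. The SDs are assumed, since the documents give none for slopes.

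- Slope SD 2, error SD 5: SE 0.387 becomes 0.347; z is 2.58 before and after; the 95% CI 0.24 to 1.76 becomes 0.22 to 1.58.
- Slope SD 3, error SD 7: SE 0.550 becomes 0.494; z is 1.82 before and after.

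A separate simulation of 2,000 trials of 530 participants (slope SD 2.5, error SD 5) gave both slopes, the difference and the standard error multiplied by 0.898, with mean z 2.443 on either axis.

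**The case against.** The strongest reply is that a bias is not shown, only a possible one. The SAP gives a reason for late tests: "the procedure required a longer visit, so it was more difficult to schedule". Failed iGFR tests could be repeated within four weeks of the result (Protocol 7.1.3), the protocol windows for these visits are skewed late (two weeks before, four after), and the upper analysis limit for Visit 16 moved from week 160 in the 2017 SAP to 178. The May 2019 SAP was written near the end of the trial, so its authors could have known the real timing. On-target visits may then be the least likely case. This stands as far as size goes: at 160/170 the iGFR factor is 0.955 and the eGFR factor 0.986. But nothing shows that mean times were 164 and 174, and if Visit 11 also ran late the loss grows again (84/160/172 gives 0.924).

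The consequence is also limited. Both arms and the confidence limits scale together, so direction and significance hold; the primary analysis and the Visit 16 iGFR analysis use visit-specific effects and are untouched. That is correct. The planning rates come from observational cohorts and were never an exact match for covariate-adjusted slopes from Visit 11 onward, so that comparison should not be pressed hard. The 0.818 corner, with Visit 11 at its latest and Visits 16 and 17 at their earliest, bounds the error and is not a plausible mean.

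A common time per visit is defensible with visit-indexed imputation, and NIDDK and the DSMB approved the 2019 SAP. The choice of a common time is not the fault; the values chosen, and the rule given for them, are. In the 2017 SAP nearly the same sentence described window boundaries, so it may simply have been carried over.

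**Conclusion.** The point holds. Table 6.3.2 contradicts its own targets, the stated rule does not yield its entries, and Visit 11 is handled differently from Visits 16 and 17. With visits on target, iGFR slopes, their difference and its limits are 10.2% too small and eGFR slopes 3.7% too small. At any combination of protocol-window limits the iGFR error is towards zero. The exact size rests on visit dates that the documents do not give: it is zero if mean times were 80/164/174, and it reverses if Visit 11 ran early while the other two ran that late. The damage is to the reported per-year estimates of two secondary endpoints, not to their p-values or to the primary result. It should be fixed.

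**What to change.** - In 6.7.2 and 6.7.4, use actual time since randomization for every observed iGFR and eGFR value.
- For imputed values, including those after ESRD that have no test date, use the mean observed time of that visit, pooled over arms so that it stays blinded. Use the target week instead if that mean lies within about one week of it; a one-week shift of Visits 16 and 17 moves the iGFR slope by about 1%.
- Apply one rule to Visits 11, 16 and 17, replace 164 and 174 in Table 6.3.2, and reword the sentence in 6.3 to name the rule used. Extending the window mid-point rule to Visit 11 would be consistent but worse: assigned times of 75/164/174 with visits on target give a factor of 0.851.
- The imputation model works by visit and ignores exact dates. As a check on mixing the two, also run each slope model once with the pooled mean times for all values.

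The cost is SAP wording and a few lines of code. The dates are already needed to assign observations to windows, and no new data are required.
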